## 5 General Considerations

The derivation of PK parameters will be performed by the IMPAACT 2017 protocol pharmacologists, as described in the PK SAP. The statistical summaries to be prepared by the statisticians are described in this Primary SAP.

Continuous variables will be summarized by N, N missing, mean, standard deviation, and quantiles of minimum, 25th percentile, median, 75th percentile, and maximum. Categorical variables will be summarized by N (%) in each category, excluding the missing category in the denominator.

For all baseline demographics and exposure analyses, results will be presented for the All Treated analysis set. The baseline value will be the latest pre-dose assessment with a non-missing value, including those from unscheduled visits. If time is not collected, Day 1 assessments are assumed to be taken prior to first dose and used as baseline. Unless otherwise stated, if baseline data are missing, no derivation will be performed and baseline will be set to missing.

All safety data will be considered from the first patient exposure to study treatment. Each participant's safety data will be summarized as: (1) the worst grade of each AE and (2) the worst grade of each AE judged to be related to study treatment.

Listings of all Grade 3 or higher AEs regardless of treatment attribution, serious AEs meeting ICH criteria assessed as related to study product(s), and AEs which resulted in permanent discontinuation of study product(s) or death will be provided. These categories of AEs will also be summarized and broken down by System Organ Class. The Division of AIDS Table for Grading the Severity of Adult and Pediatric Adverse Events (DAIDS AE Grading Table), Corrected Version 2.1, dated July 2017, will be used in this study. This table is available on the RSC website at <https://rsc.niaid.nih.gov/clinical-research-sites/daids-adverse-event-grading-tables>.

Analyses of primary and secondary outcome measures will include Cohort 1-naïve evaluable participants, as defined above. Supplementary analyses of safety and virologic outcome measures will include all participants (Cohort 1-naïve and Cohort 1 rollovers) who received study products (All Treated analysis set referenced above).

## 6 Estimands and Analysis

### 6.1 Primary Estimands and Analysis

Primary Objective 1: To assess the safety of CAB + RPV in adolescents living with HIV who are virologically suppressed through Week 24 (Cohort 2A)/Week 20 (Cohort 2B).	
Estimand	Probability of a virologically suppressed adolescent (aged 12 to <18 years) living with HIV-1, who was either exclusively treated with the combination of RPV and CAB at the final recommended dose for 24 weeks (for oral lead-in) or 20 weeks (for direct to injection), experienced a severe, potentially life-threatening, or death event attributable to CAB and/or RPV, or permanently discontinued CAB and/or RPV due to a related toxicity, having at least one event (any adverse event; severe, potentially life-threatening, or death event; severe, potentially life-threatening, or death event assessed as related to CAB and/or RPV; serious adverse event assessed as related to CAB and/or RPV; permanent discontinuation of CAB and/or RPV due to adverse event assessed as related to CAB and/or RPV; death due to adverse event assessed as related to CAB and/or RPV).
Treatment	30 mg CAB + 25 mg RPV once daily orally for four weeks followed by IM injections of 600 mg CAB LA + 900 mg RPV LA (first and second injections four weeks apart with subsequent injections every eight weeks) or direct to IM injections of 600 mg CAB LA + 900 mg RPV LA (first and second injections four weeks apart with subsequent injections every eight weeks).
Target population	Analysis set
Virologically suppressed children and adolescents 12 to <18 years of age living with HIV-1 exclusively treated with the combination of RPV and CAB at the final recommended dose for either 24 weeks (for oral lead-in) or 20 weeks (for direct to injection).	
Participants who are exclusively treated with the combination of RPV and CAB at the final recommended dose and either completed all treatment regimen through the Week 24 (Cohort 2A)/Week 20 (Cohort 2B) visit or experienced any of the following:
 

• death that is attributable to the study product(s), OR

• study product-related Grade 3 or higher adverse event (excluding injection-site AEs), OR

• permanent discontinuation from treatment due to study product-related toxicities (regardless of grade) during these weeks of

	treatment.
Variable(s)	Outcome measure(s)
Occurrence of each of the following through 24 weeks (for oral lead-in) or 20 weeks (for direct to injection):  
 
• Any adverse event
 
• Severe, potentially life-threatening, or death event
 
• Severe, potentially life-threatening, or death event assessed as related to CAB and/or RPV
 
• Serious adverse event related to CAB and/or RPV
 
• Permanent discontinuation of CAB and/or RPV due to adverse event assessed as related to CAB and/or RPV
 
• Death due to adverse event assessed as related to CAB and/or RPV
 
	Occurrence of each of the following through Week 24 (Cohort 2A)/through Week 20 (Cohort 2B):  
 
• Any adverse event, regardless of grade
 
• Grade 3 or higher adverse event
 
• Grade 3 or higher adverse event assessed as related to study product(s)
 
• Serious adverse event meeting ICH criteria assessed as related to study product(s)
 
• Permanent discontinuation of study product due to adverse event assessed as related to study product(s)
 
• Death due to adverse event assessed as related to study product(s)
 

Handling of intercurrent events	Handling of missing data
The following intercurrent events are relevant to the estimand:  
 
1. Discontinuation of CAB and/or RPV due to toxicity
 
2. Death related to CAB and/or RPV
 
 
These intercurrent events (1, 2) will be addressed using a while on treatment strategy.
 
 
3. Discontinuation of CAB and/or RPV due to non-toxicity reasons
 
4. Death unrelated to CAB and/or RPV
 
 
These intercurrent events (3, 4) will be addressed using a principal stratum approach.
	Missing data will be addressed using a “complete case” approach, defined per outcome measure.
Population-level summary measure	Analysis approach
Probability of having at least one event (any adverse event; severe, potentially life-threatening, or death event; severe, potentially	Proportion of participants with at least one event (any adverse event; Grade 3 or higher adverse event; Grade 3 or higher

life-threatening, or death event assessed as related to CAB and/or RPV; serious adverse event assessed as related to CAB and/or RPV; permanent discontinuation of CAB and/or RPV due to adverse event assessed as related to CAB and/or RPV; death due to adverse event assessed as related to CAB and/or RPV) through 24 weeks (for oral lead-in) or 20 weeks (for direct to injection).	adverse event assessed as related to study product(s); serious adverse event meeting ICH criteria assessed as related to study product(s); permanent discontinuation of study product due to adverse event assessed as related to study product(s); death due to adverse event assessed as related to study product(s)) through Week 24 (Cohort 2A)/through Week 20 (Cohort 2B), bounded by an exact (Clopper-Pearson) 95% CI.
---	--

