## **4 Analysis Sets**

The following analysis sets are defined:

**All Treated:** All participants who took at least one dose of any study product in Cohort 2

**Evaluable:** For analysis purposes, evaluable participants will be defined as having been treated exclusively on the final recommended dose and either (1) having completed all treatment regimen through Week 24 (Cohort 2A)/Week 20 (Cohort 2B) or (2) having experienced any of the following:

- death that is attributable to the study product(s), OR
- study product-related Grade 3 or higher event (excluding injection-site AEs), OR
- permanently discontinued from treatment due to study product-related toxicities (regardless of grade) during these weeks of treatment.

Notes:

- An additional requirement for inclusion in the primary analyses for Cohort 2 is that the participants must be directly accrued to this cohort and be exclusively treated with the combination of the two study products; this will be approximately 70 participants.

- Oral bridging in Cohort 2 will not be counted as a substitute for an injection but as long as the recommended number of injections were given through Week 24/Week 20, even if they were out of window, the participant will be considered evaluable.

**Cohort 1 Rollover:** Cohort 2 participants who were previously enrolled to Cohort 1.

**Cohort 1-Naïve:** Cohort 2 participants who were enrolled directly to Cohort 2 without prior participation in Cohort 1.

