
Variable(s)
 
Occurrence of virologic failure through 24/48 weeks (oral lead in)/through 20/44 weeks (direct to injection):
 
 
• Plasma HIV-1 RNA <math>\geq</math>50 copies/mL
 
• Plasma HIV-1 RNA <math>\geq</math>200 copies/mL
 
	
Outcome measure(s)
 
Occurrence of virologic failure through Week 24 and through Week 48 (Cohort 2A)/through Week 20 and through Week 44 (Cohort 2B):
 
 
• Plasma HIV-1 RNA <math>\geq</math>50 copies/mL, per snapshot algorithm
 
• Plasma HIV-1 RNA <math>\geq</math>200 copies/mL, per snapshot algorithm
 

Handling of intercurrent events
 
The following intercurrent events are relevant to the estimand:
 
 
1. Discontinuation of CAB and/or RPV due to toxicity
 
2. Death related to CAB and/or RPV
 
 
These intercurrent events (1, 2) will be addressed as specified in the snapshot algorithm.
 
 
3. Discontinuation of CAB and/or RPV due to non-toxicity reasons
 
	
Handling of missing data
 
Missing data will be handled as described in the snapshot algorithm.

4. Death unrelated to CAB and/or RPV  These intercurrent events (3, 4) will be addressed using a principal stratum approach.	
Population-level summary measure	Analysis approach

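### The intercurrent-event row keeps anyone who stops CAB/RPV for toxicity, but the analysis set keeps only related-toxicity stops, so the any-AE and Grade 3+ estimates depend on attribution

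*SAP*

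**What the plan says.** The primary estimand table in SAP Section 6.1 lists four intercurrent events.

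- Event 1 is "Discontinuation of CAB and/or RPV due to toxicity" and event 2 is related death. For both, "These intercurrent events (1, 2) will be addressed using a while on treatment strategy".
- Event 3 is "Discontinuation of CAB and/or RPV due to non-toxicity reasons" and event 4 is "Death unrelated to CAB and/or RPV". For both, "These intercurrent events (3, 4) will be addressed using a principal stratum approach".

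Deaths are divided by relatedness and toxicity stops are not. The SAP does not define toxicity.

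Section 4 makes a participant on the final recommended dose evaluable by completing treatment through Week 24 (Cohort 2A) or Week 20 (Cohort 2B). An earlier stopper qualifies only with a product-related death, a product-related Grade 3+ event other than at the injection site, or having "permanently discontinued from treatment due to study product-related toxicities (regardless of grade) during these weeks of treatment". The analysis-set row in 6.1 repeats these routes, and the estimand sentence also speaks of a related toxicity.

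Section 6.2.1 carries the same pair of rules to Week 48/44. Section 6.2.2 repeats them for the virologic estimand, except that "These intercurrent events (1, 2) will be addressed as specified in the snapshot algorithm".

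Section 5 bases the primary and secondary analyses on Cohort 1-naïve evaluable participants. Section 3.1 lists six primary outcomes. Two of them, any AE and Grade 3 or higher AE, have no attribution condition.

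**The concern.** One table gives two answers for the same participant. Someone who stops before Week 24/20 because of an AE judged unrelated falls under event 1 as worded, and so should contribute data up to the stop. The same person meets none of the admission criteria, and so is not in the analysis set.

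This affects the two outcomes defined without regard to attribution. If an open-label judgement of relatedness decides whether the participant is in the denominator, an all-cause proportion becomes partly conditional on attribution. Grade 3 or higher AE is also the outcome on which Table 1 in Section 2.4 is built. If the conflict is left until data are in hand, the choice of who enters the primary denominator could be made with knowledge of the events.

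**Working it through.** **The rules side by side, for a Cohort 1-naïve participant who stops before Week 24/20**

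| Reason for the early stop | Intercurrent-event row, 6.1 | Analysis set, Sections 4 and 6.1 |
|---|---|---|
| Related AE | Event 1: kept, while on treatment | Kept |
| Unrelated AE, no other criterion met | Event 1: kept, while on treatment | Excluded |
| Non-toxicity reason, no other criterion met | Event 3: principal stratum | Excluded |
| Unrelated death, no other criterion met | Event 4: principal stratum | Excluded |

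Only the second line conflicts. A participant in that line who also had a related Grade 3+ event away from the injection site is admitted by that route.

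**Direction of the effect**

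Let x of n evaluable participants have the event. Let m unrelated-AE stoppers be excluded, of whom k had the event. Restoring them changes x/n to (x+k)/(n+m), which is higher than x/n exactly when k/m exceeds x/n.

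- Any AE: every such stopper has an AE, so k = m. Exclusion can only lower the proportion, or leave it at 100%.
- Grade 3 or higher: exclusion lowers the proportion when the stopper had a Grade 3+ event. For a stopper with only Grade 1–2 events it slightly raises any non-zero proportion: restoring one such person takes 14/70 = 20.0% to 14/71 = 19.7%.

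**Reproducing Table 1**

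The exact 95% limits are Beta quantiles: the 2.5% point of Beta(x, n−x+1) and the 97.5% point of Beta(x+1, n−x). For x = 0 the lower limit is 0.

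| Case | Computed | Table 1 |
|---|---|---|
| 0/70 | 0 to 0.0513 | 0.00, 0.05 |
| 0/100 | 0 to 0.0362 | 0.00, 0.04 |
| 14/70 | 0.1139 to 0.3127 | 0.11, 0.31 |
| 20/100 | 0.1267 to 0.2918 | 0.13, 0.29 |

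All four agree.

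**Illustration for Grade 3 or higher**

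The SAP gives no figure for k. Here k is assumed, and every restored stopper is assumed to have a Grade 3+ event (m = k). The calculation is (x+k)/(70+k).

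| k | Starting from 14/70 | Starting from 0/70 |
|---|---|---|
| 0 | 14/70 = 20.0% (11.4 to 31.3) | 0/70 = 0% (0 to 5.1) |
| 1 | 15/71 = 21.1% (12.3 to 32.4) | 1/71 = 1.4% (0.0 to 7.6) |
| 2 | 16/72 = 22.2% (13.3 to 33.6) | 2/72 = 2.8% (0.3 to 9.7) |
| 4 | 18/74 = 24.3% (15.1 to 35.7) | 4/74 = 5.4% (1.5 to 13.3) |

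From zero events, one participant raises the upper limit from 5.1% to 7.6%, about half as much again (7.60/5.13 = 1.48).

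**The case against.** **Toxicity may mean related toxicity.** The list pairs the toxicity stop with related death and the non-toxicity stop with unrelated death, and the estimand sentence in the same table says related. On that reading an unrelated-AE stop belongs to event 3 and the contradiction disappears. The reading is possible. Against it, the list divides deaths by relatedness but not toxicity stops, and the SAP adds the qualifier elsewhere when it wants it. Even if accepted, it leaves the all-cause outcomes selected by attribution.

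**Who is analysed is not in doubt.** A while-on-treatment strategy says which data count; it does not admit anyone to a set. Sections 4 and 5 settle the set. This stands, and it is why the exclusion is the practical result.

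**The events are not lost.** A reader might infer that the plan deletes them. It does not. Section 5 lists every Grade 3+ AE whatever its attribution, and the All Treated supplementary analysis in 6.1 handles all intercurrent events while on treatment. The repair is partial: All Treated pools up to 55 Cohort 1 rollovers (Section 2.1), the missing-data sensitivity analyses of the primary analysis cover evaluable participants only, and none of the analyses described returns these participants to a Cohort 1-naïve estimate.

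**The bias need not favour the product.** A reader might infer that exclusion always lowers the Grade 3+ rate. The 14/71 example shows otherwise.

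**The virologic result is not shown to be flattered.** Under the snapshot in Attachment 2, a safety withdrawal without an in-window viral load is classed as no virologic data. Unless another row applies, restoring that person only enlarges the denominator.

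**The size is assumed.** This is correct. The gap between up to 100 enrolled and about 70 evaluable says nothing about unrelated-AE stops. At 20%, one participant moves the estimate by 1.1 points inside an interval about 20 points wide, and the SAP sets no pass mark for this rate.

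**Conclusion.** The rows do not match as written, and they should be reconciled before database lock. As the set governs, Cohort 1-naïve participants who stop early for an unrelated AE, and meet no other criterion, drop out of the evaluable-set estimates of any AE and Grade 3 or higher AE at Week 24/20. The same holds at Week 48/44.

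For any AE the exclusion cannot raise the proportion. For Grade 3 or higher the direction depends on whether the stopper had such an event. With an assumed one to four who did, 20.0% becomes 21.1% to 24.3%. With none, the estimates do not move. No shift in the virologic result is claimed in either direction.

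The point is moderate: it concerns the definition of two primary outcomes in a non-comparative study, and the planned listings and All Treated analysis already limit the harm.

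**What to change.** Use the same term in the intercurrent-event row, the estimand sentence and the analysis set in Sections 4, 6.1, 6.2.1 and 6.2.2, and define it.

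**Preferred.** For the two attribution-free safety outcomes, include in the Cohort 1-naïve analysis set participants who permanently discontinue because of an adverse event, whether or not it is judged related, with events counted up to discontinuation. The outcome for discontinuation due to a related AE stays unchanged. So can the definition used for the accrual target of about 70 evaluable.

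**Alternative, if the sponsor keeps the related-only set.** Word event 1 as related toxicity, move unrelated-AE stops to event 3, and also report the any-AE and Grade 3+ proportions for all treated Cohort 1-naïve participants.

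**Cost.** The change is to SAP text and to the derivation of one analysis set. Whether the protocol needs a matching edit cannot be judged here, because it is not at hand. A few participants with less than full exposure enter the denominator, and the Grade 3+ estimate may be slightly less favourable.

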Participants who prematurely discontinue injectable study product permanently, will continue on-study for an additional 48 weeks after their last study product injection, per the long-term safety and washout PK follow-up (LSFU) schedule.

The sample size for Cohort 2 will be up to 155 adolescents in total. Up to 100 adolescents, who had not previously participated in Cohort 1 (i.e., Cohort 1-naïve), will be enrolled to achieve approximately 70 evaluable. Cohort 2A participants will receive the final recommended oral doses followed by the LA doses of CAB and RPV. Cohort 2B participants will receive the final recommended LA doses of CAB and RPV. Adolescents who participated in Cohort 1 (i.e., Cohort

1 rollovers; up to 55) may continue study participation in Cohort 2, if eligible, in addition to the up to 100 Cohort 2 participants newly enrolled to the study.

At the Week 96/92 visit, Cohort 2A Step 4 and Cohort 2B Step 5 participants continuing to receive injectable CAB LA + RPV LA external to the protocol will exit the study. Section 14.11 of protocol Version 4.0 has more information regarding post-trial access to study products. Participants who discontinue injectable CAB LA + RPV LA at the Week 96/92 visit will not exit the study. These participants will be followed for 48 weeks per the LSFU visit schedule.

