## 2.5 Overview of Formal Interim Monitoring

Interim Analysis #1 took place on 19 June 2020. Based upon study data from the first seven evaluable participants in each Cohort 1C and Cohort 1R, the IMPAACT 2017 CMC concluded that dosing regimens for oral CAB, CAB LA, and RPV LA achieved the PK targets as per protocol Version 2.0. Additionally, the LSFU PK results indicate both CAB and RPV concentrations maintain pharmacologically relevant concentrations, above the IC90, for several weeks after their final IM injection. This interim analysis confirmed that the doses implemented for both Cohort 1C and Cohort 1R passed the safety guidelines in Section 9.5.1.3 of protocol Version 2.0 for the first seven evaluable participants in each group. The CMC concluded that protocol criteria to open Cohort 2 to Cohort 1 graduates had been met, and the SMC agreed with this conclusion.

Interim Analysis #2 was conducted on 18 April 2022. The doses implemented for both Cohort 1C and Cohort 1R passed the safety guidelines per Section 9.5.1.3 of protocol Version 3.0. The CMC concluded that the analysis supported opening Cohort 2 accrual to participants who were not previously enrolled in Cohort 1, and the SMC agreed with this conclusion.

A final analysis of Cohort 1 data will be performed to confirm the final doses for Cohort 2 (using Version 2.0 of the Primary SAP).

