## 3 Outcome Measures

### 3.1 Primary Outcome Measures

Safety through Week 24 (Cohort 2A)/through Week 20 (Cohort 2B):

- Any adverse event, regardless of grade
- Grade 3 or higher adverse event
- Grade 3 or higher adverse event assessed as related to study product(s)
- Serious adverse event meeting ICH criteria assessed as related to study product(s)
- Permanent discontinuation of study product due to adverse event assessed as related to study product(s)
- Death due to adverse event assessed as related to study product(s)

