### **3.2 Secondary Safety and Viral Suppression Outcome Measures**

Safety through Week 48 (Cohort 2A)/through Week 44 (Cohort 2B):

- Any adverse event, regardless of grade
- Grade 3 or higher adverse event
- Grade 3 or higher adverse event assessed as related to study product(s)
- Serious adverse event meeting ICH criteria assessed as related to study product(s)
- Permanent discontinuation of study product due to adverse event assessed as related to study product(s)
- Death due to adverse events assessed as related to study product(s)

Virologic activity through Week 24 and through Week 48 (Cohort 2A)/through Week 20 and through Week 44 (Cohort 2B):

- Plasma HIV-1 RNA  $\geq 50$  copies/mL, per snapshot algorithm
- Plasma HIV-1 RNA  $\geq 200$  copies/mL, per snapshot algorithm

NOTE: PK outcome measures are described in the PK SAP.

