### Supplementary Analyses

Supplementary analyses for the primary outcome measures will include all participants (Cohort 1-naïve and Cohort 1 rollovers) who received study products. All intercurrent events will be addressed using a while on treatment strategy, and missing data will be handled using a complete case approach. Because this approach assumes data are missing completely at random, we will use multiple imputation that assumes missing at random as a sensitivity analysis. We will create 100 imputed data sets using appropriate FCS model and combine results using Rubin's rules. We will also present estimates assuming "best case" (i.e., probability of event = 0) and "worst case" (i.e., probability of event = 1) scenarios.

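### The safety estimands use a while-on-treatment strategy with no defined end of treatment, for a long-acting product whose outcomes are worded through a fixed week

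*SAP*

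**What the plan says.** Four parts of the SAP bear on this.

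- **Strategy.** Under the handling of intercurrent events in section 6.1, for discontinuation due to toxicity and for related death: "These intercurrent events (1, 2) will be addressed using a while on treatment strategy". Section 6.2.1 repeats this for the Week 48/44 safety estimand. Non-toxicity discontinuation and unrelated death go to a principal stratum approach. The supplementary safety analyses in the All Treated set (sections 6.1 and 6.2.1) state: "All intercurrent events will be addressed using a while on treatment strategy, and missing data will be handled using a complete case approach".
- **Outcomes.** Sections 3.1 and 3.2, and the variable and summary-measure rows of the estimand tables, define each outcome as occurrence through Week 24 (Cohort 2A) or Week 20 (Cohort 2B), and through Week 48 or Week 44.
- **Exposure after stopping.** Section 2.5 reports from the first interim analysis that "both CAB and RPV concentrations maintain pharmacologically relevant concentrations, above the IC90, for several weeks after their final IM injection".
- **Follow-up after stopping.** Section 2.1 says that participants who permanently stop the injectable product early "will continue on-study for an additional 48 weeks after their last study product injection", on the long-term safety and washout PK schedule (LSFU).

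Section 5 takes safety data from first exposure onwards and gives no end. No section defines the end of the on-treatment period, whether as the last dose, the decision to stop, the next due injection or a period after the last injection.

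**The concern.** A while-on-treatment strategy ordinarily uses outcome data only up to the intercurrent event. For a daily tablet, stopping and the end of exposure are close together. For injections given eight weeks apart they are not, as section 2.5 itself records. A participant who stops for toxicity and then, still exposed and still followed, has a first related Grade 3 or higher event before Week 24/20 would not count for that outcome.

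These are the people whom section 4 deliberately keeps in the evaluable set because they had toxicity. If their record is cut at discontinuation, the reported proportions for the more serious outcomes can only go down, never up. For rare outcomes such as related serious adverse event or related death, one participant changes what is reported. The planned safety sensitivity analyses would not reveal this: they vary only the treatment of missing data, and none is stated to count events after stopping.

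**Working it through.** **Reproducing the plan's own figures.** The exact 95% limits are the Beta(k, n−k+1) quantile at 0.025 and the Beta(k+1, n−k) quantile at 0.975, with lower limit 0 when k = 0.

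| Events/N | Computed | SAP Table 1 |
|---|---|---|
| 0/70 | 0 to 0.0513 | 0.00, 0.05 |
| 0/100 | 0 to 0.0362 | 0.00, 0.04 |
| 14/70 | 0.1139 to 0.3127 | 0.11, 0.31 |
| 20/100 | 0.1267 to 0.2918 | 0.13, 0.29 |

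All four rows agree, so no arithmetic error is involved.

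**Time that could go uncounted.** Section 2.1 gives two injections four weeks apart, then one every eight weeks up to Week 96 (2A) or Week 92 (2B). Counting back, and taking the four-week oral lead-in, the nominal injection weeks are 4, 8, 16, 24, … in 2A and 0, 4, 12, 20, … in 2B. Time at risk of being dropped = end of window − week of last injection:

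| Last injection | Primary, 2A | Primary, 2B | Secondary, 2A | Secondary, 2B |
|---|---|---|---|---|
| 1st | 24−4 = 20 | 20−0 = 20 | 48−4 = 44 | 44−0 = 44 |
| 2nd | 24−8 = 16 | 20−4 = 16 | 48−8 = 40 | 44−4 = 40 |
| 3rd | 24−16 = 8 | 20−12 = 8 | 48−16 = 32 | 44−12 = 32 |

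These are maxima, measured from the last injection. If counting ends at a later decision to stop, less is lost. Under the eight-week spacing, the last injection and the next due date differ by up to eight weeks, so the undefined cut-off alone can change which events count.

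**Which outcomes are exposed.** Someone who stops for a related adverse event has already met the any-adverse-event and related-discontinuation outcomes, provided the period runs at least to the decision to stop. If that event was Grade 3 or higher, both Grade 3 outcomes are met too. What can be missed is a first later event in a category not yet met: Grade 3 or higher, related Grade 3 or higher, related serious adverse event, or related death after an earlier discontinuation. A related death by itself only ends observation and loses nothing.

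**Effect on a reported proportion.** The number of participants affected is not in the SAP, so m below is an assumption. With N = 70 (section 4), each one is worth 1/70 = 1.4 points.

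| m missed | From 0/70 (upper limit 5.1%) | From 14/70 (20.0%, 11.4 to 31.3%) |
|---|---|---|
| 1 | 1.4% (0.04 to 7.7%) | 21.4% (12.5 to 32.9%) |
| 2 | 2.9% (0.3 to 9.9%) | 22.9% (13.7 to 34.5%) |
| 3 | 4.3% (0.9 to 12.0%) | 24.3% (14.8 to 36.0%) |

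**The case against.** The best reply is that the SAP nowhere says that counting stops at discontinuation. The on-treatment period is undefined, the outcomes are worded through a fixed week, section 5 sets no end to safety data, and coding detail is left to an Analysis Implementation Plan that is not at hand. A period long enough to cover post-injection exposure would fit the text. This stands as far as it goes: truncation is the ordinary meaning of the named strategy, not a sentence in the plan. But both readings need a correction. If counting stops, later toxicity under continuing exposure is left out of the estimates; if it runs to the end of the window, the strategy is misnamed and is in fact treatment policy.

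Three stronger inferences are tempting, and the document does not support them.

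- *The signal disappears from the report.* Section 5 promises listings and System Organ Class summaries of all Grade 3 or higher events, related serious events, and events leading to discontinuation or death, with no on-treatment limit attached. Later events may well appear there. Only the estimated proportions would omit them.
- *The loss can be sized from the gap between 100 enrolled and about 70 evaluable.* Toxicity discontinuers are evaluable under section 4, so they are not in that gap. Participants can also be non-evaluable without having stopped, for example through a missed injection. The summary measure is a proportion of participants, not person-time.
- *All 48 weeks of follow-up are lost.* Only the part before Week 24/20 or Week 48/44 bears on these outcomes.

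Two further points are fair. The 48-week follow-up in section 2.1 is for those who stop injections, so a Cohort 2A participant who stops during the oral lead-in has no depot and is not placed on that schedule by the text. While-on-treatment is also a recognised strategy for safety, so the objection is to its use here, undefined and as the only approach for these participants.

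**Conclusion.** The concern holds as a fault of a named rule without a defined end, in conflict with the outcome wording and with the SAP's own statements on persistence and follow-up. Followed in its usual meaning, it can only lower the reported proportions for the four more serious outcomes, and no planned safety analysis is stated to count the later events.

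Its reach is limited. In the primary and secondary analyses it concerns toxicity discontinuers only, and only outcomes not already met. In the All Treated supplementary analyses it extends to all discontinuers. Up to 20 weeks (primary) or 44 weeks (secondary) after the last injection are at stake, on the nominal schedule and if counting ended at that injection. The effect is 1.4 points per participant missed at N = 70. Because the number missed cannot be derived from the document, no overall bias can be stated. It should be corrected before analysis.

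**What to change.** 1. For all safety outcomes, count every adverse event with onset through Week 24/20, and through Week 48/44, whether or not study product was stopped (a treatment policy strategy for discontinuation). Use LSFU data where participants are on that schedule, and state how those who stop during the oral lead-in are followed for this purpose.
2. Make the intercurrent-event rows in sections 6.1 and 6.2.1, and both supplementary safety analyses, agree with the outcome wording.
3. Keep while-on-treatment as a supplementary display, with the end of the period defined relative to the last dose or injection and the choice justified.

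The cost is SAP wording and the matching programming. For participants who stop injections, follow-up is already planned, although the LSFU evaluations are not listed in the SAP and should be checked. The downside is small: some any-grade or unrelated Grade 3 or higher events may arise on the next regimen. The relatedness outcomes separate these.
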